|--------------------------------|--|
| TITLE | The MAGNIFI Trial: Metastasis assessment with Gallium-68 PSMA and Nanoparticle Imaging Fusion International |
| SHORT TITLE | Magnifi Trial |
| VERSION NO. | 2.4 24 th January 2019 |
| SPONSOR | The Garvan Institute of Medical Research [name] |
| INDICATION | Diagnosis and treatment of lymph node metastases in men with prostate cancer |
| OBJECTIVES | 
1. To compare “Combidex” Nanoparticle-Magnetic Resonance Lymphography (Nano MRL) and 68Ga-PSMA positron emission tomography (PET) to the gold standard and current practice; the histology of pelvic lymph node dissection, to locate the position of lymph nodes
 
2. Determine whether concordance of these two imaging technologies (68Ga-PSMA PET - functional imaging, and Nano MR - anatomical imaging) is worse, better or equal to lymph-node dissection
 |
| TRIAL DESIGN | An investigator initiated, prospective, non-randomized study |
| PLANNED NUMBER OF PARTICIPANTS | 120 participants will be recruited over a two year period; 60 participants from St Vincent’s Hospital Sydney and 60 participants from the Wesley Hospital Brisbane |
| TARGET POPULATION | Men diagnosed with prostate cancer with and without suspicion of lymph node involvement but have yet to undergo a radical prostatectomy. |
| INCLUSION CRITERIA | 
 • Male, aged 18 years or over • Confirmed adenocarcinoma of prostate and at least clinical stage T3A and/or Gleason sum $\geq 4+3=7$, or preoperative PSA ≥ 15 ng/ml and planned radical prostatectomy • Suspected lymph node involvement pre- radical prostatectomy based on Briganti nomogram $\geq 10\%$. • Suitable for radical prostatectomy and pelvic lymph node dissection, as per institutional guidelines and not yet treated pre-prostatectomy • Subject is able to understand and willing to sign the participant information statement and consent form • Subject is expected to remain available for 24 months of clinic visits |
| EXCLUSION CRITERIA | 
 • Past history any other type of cancer (except skin cancer). • Previous treatment for prostate cancer (surgery, radiotherapy, chemotherapy, hormone androgen deprivation therapy) • Proven bony metastatic disease, visceral metastases or lymph node metastases above the level of the aortic bifurcation |

| | |
|--|---|

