3.2. STUDY GROUPS

There will only be one study group and it will consist of intermediate and high-risk cancer patients with a >10% probability on LN where LND would currently be performed as part of the treatment protocol (guided by the updated Briganti nomogram) [34]

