After all imaging is complete, Patients will undergo radical prostatectomy and extended pelvic lymph node dissection, as clinically indicated, with all dissected lymph node packets being dissected and labelled. Approximately 6 packets of lymph nodes are expected per patients, each hemipelvis providing node packets from the external iliac vein, obturator fossa and internal iliac vessels as described by Bader et al. Specifically, all fibro-fatty tissue along the external iliac vein along the pelvic sidewall, caudal to the femoral canal and proximally to the bifurcation of the common iliac artery will be dissected and removed to be labelled as 'external iliac vein nodal packet'. All fibro-fatty tissue within the obturator fossa along the obturator muscle, skeletonising the obturator nerve and vessels will be labelled 'obturator fossa'. Finally the internal iliac artery and internal iliac vein will be skeletonised, all tissue removed from this dissection will be labelled 'internal iliac vessels'. Suspicious lymph nodes detected on nano-MRL or PSMA will be additionally targeted for resection during lymph node dissection, particularly presacral and mesorectal nodes. Specifically identified nodes in the mesorectal plane may be localised with percutaneous hookwire prior to dissection. At the discretion of the operating surgeons, and in consultation, suspicious nodes outside this template may also be resected if doing so does not place the patient at significant additional risk. Each nodal packet removed will also be qualified as either 'complete' or 'incomplete' for imaging vs histology concordance analysis. The reason for 'incomplete' dissection will be recorded.

An accredited robotic urological surgeon will perform the pelvic lymph node dissection. All participating urologists will undergo external video analysis and independent validation prior to commencement of the MAGNIFI trial.

4. *Histopathology*

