We will calculate the CONCORDANCE rate for positive nodes in each packet with their corresponding region on imaging, both against each individual imaging modality and against a summed score from both imaging techniques. Sensitivity, specificity, negative predictive values (NPVs), and positive predictive values (PPVs) will be reported [31, 32]. The maximum likelihood estimates (MLEs) of PPV and NPV will be calculated from the MLEs of the sensitivity, specificity, and prevalence rate. Hierarchical modelling will be used to test for concordance between matched results from each packet.

Secondary outcome of interest is quality of life and the complications. As part of initial longitudinal analyses quality of life (as measured using EORTC-QLQ-C30) will be evaluated using one-way ANOVA. To examine differences in quality of life scores between the two groups (standard eLND versus super-eLND), baseline characteristics will be compared between groups to assess whether the groups are balanced using Chi-square tests and Fisher's exact tests. The additional analysis involves comparing the change in quality of life scores (worsened, stable or improved quality of life) from baseline to 2 and 6 months between the groups using Chi-square tests and Fisher's exact tests. Similar method will be used evaluating the differences in the complication score.

c) Interim Analysis:

An analysis of the data will be performed after every 10 patients have completed imaging and pelvic lymph node dissection. This will allow the trial statistician and data monitoring committee to identify any problems or discrepancies with data collection and recording, in addition to identifying any possible technical issues that might jeopardise

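### Quality of life and complications are compared between two dissection groups that this one-group trial never defines; the contrast is confounded by disease extent, its three-level test loses power, and its instrument and 2-month visit are not scheduled

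*Protocol*

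**What the plan says.** All references are to the protocol.

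- **Design.** The synopsis describes "An investigator initiated, prospective, non-randomized study", and section 3.2 states "There will only be one study group".
- **Comparison.** Section 7 b) makes quality of life and complications the secondary outcome of interest. It first says "quality of life (as measured using EORTC-QLQ-C30) will be evaluated using one-way ANOVA". It then sets out "To examine differences in quality of life scores between the two groups (standard eLND versus super-eLND"), with chi-square and Fisher tests to see whether the two groups are balanced at baseline.
- **Additional analysis.** This is "comparing the change in quality of life scores (worsened, stable or improved quality of life"), from baseline to 2 and 6 months, again by chi-square and Fisher tests. Complication scores are to be handled in a similar way.
- **How a dissection becomes wider.** Section 5.2, item 3, gives every man the template dissection and adds: "Suspicious lymph nodes detected on nano-MRL or PSMA will be additionally targeted for resection during lymph node dissection, particularly presacral and mesorectal nodes". It continues: "At the discretion of the operating surgeons, and in consultation, suspicious nodes outside this template may also be resected", on condition that the patient is not put at significant extra risk.
- **What is collected.** Section 5.2, item 7, and the synopsis schedule EPIC at baseline, 6 weeks, 3 months, 6 months, 1 year and then yearly. No other quality-of-life instrument is scheduled.

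**The concern.** Section 7 b) treats extent of dissection as if it defined two arms, but nothing in the design creates them. Super-eLND occurs only in that paragraph and no rule places a man in either group, so the exposure would have to be defined after the fact.

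On any natural reading of the term, the men with wider surgery are those whose scans looked suspicious and whose surgeon judged the extra resection acceptable. They differ in disease extent, and probably in fitness, before the first incision. A difference in quality of life or complications could then be taken for an effect of wider surgery when it reflects worse disease. That matters because section 1.2 argues that imaging could spare or target dissection, and a result by extent of surgery would feed directly into that argument.

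Two further faults sit in the same paragraph. Reducing change to three levels throws away information. And the named instrument and one of the two named time points do not match what the trial collects.

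**Working it through.** The protocol gives no sample size, power, effect size, SD, category limits or group split for this comparison, so there is no stated figure to reproduce. N = 120 comes from section 3.3. The two-sided 0.05 level is stated for the primary test and assumed here. All other inputs below are assumptions.

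**1. Confounding.** Suppose surgery has no effect at all, and node-positive men change 0.5 SD worse. Suppose node-positive men make up 60% of a super-eLND group of 36 and 15% of a standard group of 84.
- Spurious difference = 0.5 × (0.60 − 0.15) = 0.225 SD.
- SE = √(1/84 + 1/36) = 0.199, so z = 0.225/0.199 = 1.13.
- Rejection ≈ Φ(1.13 − 1.96) ≈ 20%, instead of 5%.

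With 80% v 10% node-positive, the spurious difference is 0.35 SD and rejection about 42%. Letting the nodal effect run from 0.3 to 0.8 SD moves rejection from about 10% to about 80%. A baseline balance test changes none of this, because it detects imbalance without adjusting for it.

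**2. Three levels against the continuous score.** Assume a true difference of 0.5 SD, a stable band of ±0.5 SD, correlation r between baseline and follow-up, and no confounding.
- SD of change = √(2(1 − r)): 1.00 at r = 0.5 and 0.775 at r = 0.7.
- At r = 0.5 the worsened/stable/improved proportions are 0.309/0.383/0.309 in one group and 0.159/0.341/0.500 in the other. With 90 v 30 the chi-square noncentrality is 4.28 on 2 df, which gives 44% power. At r = 0.7 it is 7.05, which gives 66%.
- Baseline-adjusted score (ANCOVA): residual SD = √(1 − r²). At 90 v 30 and r = 0.5, SE = √(0.75 × (1/90 + 1/30)) = 0.183, and Φ(0.5/0.183 − 1.96) ≈ 78%.

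| Split | r | Three-level chi-square | Continuous change, unadjusted | Baseline-adjusted score |
|---|---|---|---|---|
| 90 v 30 | 0.5 | 44% | 66% | 78% |
| 90 v 30 | 0.7 | 66% | 86% | 91% |
| 60 v 60 | 0.5 | 56% | 78% | 89% |
| 60 v 60 | 0.7 | 79% | 94% | 97% |

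These are large-sample approximations. Simulation gives about 44–66% against 76–91% (90 v 30) and 57–80% against 88–96% (60 v 60). The middle column splits the gap. At 90 v 30 and r = 0.5, categorising costs 66 − 44 = 22 points and baseline adjustment gains 78 − 66 = 12.

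**3. Cost of adjusting for imaging.** If wider dissection occurs only in imaging-positive men, an imaging-adjusted contrast is estimated within those men. Take 30 with wider dissection among an assumed 40 to 60 imaging-positive men.
- 30 v 10, r = 0.5: SE = √(0.75 × (1/30 + 1/10)) = 0.316, and Φ(0.5/0.316 − 1.96) ≈ 35%.
- 30 v 30, r = 0.7: SE = √(0.51 × (1/30 + 1/30)) = 0.184, and Φ(0.5/0.184 − 1.96) ≈ 77%.

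Simulation puts the range slightly lower, at about 33–74%.

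**4. Instrument and visits, side by side.** Section 7 b) analyses EORTC-QLQ-C30 change at 2 and 6 months. The schedule collects EPIC at 6 weeks, 3 months, 6 months and later. A 2-month clinic review exists (section 5.2, item 6), but no questionnaire is attached to it. Only the 6-month time point coincides, and there the instrument differs.

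**The case against.** The best counter-case is that covariates, longitudinal models and response limits are commonly left to a statistical analysis plan. On that footing, a missing covariate list is not a defect. This stands, and the point does not rest on it. It rests on what section 7 b) does state: two groups that section 3.2 excludes, balance testing as the only safeguard named, a chi-square on three levels, and an instrument and visit that are not scheduled.

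It is also fair to say that quality of life is absent from the objectives and the endpoint list, that no causal claim is made, and that the primary accuracy analysis is untouched. That limits the weight of the point.

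Stronger readings are tempting, and the protocol does not support them:

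- *That the ANOVA wastes power too.* Analysing a continuous score loses nothing by categorising. At 90 v 30 its power is about 64–86% under the same assumptions. The three-level test is called the additional analysis, so a real difference is not left to that test alone.
- *That repeated scores are wrongly treated as independent.* The ANOVA factor is not named and nothing says visits are pooled. A group comparison at one visit uses each man once.
- *That the adjusted analysis will deliver the 76–91% shown.* That figure assumes no confounding and no imaging adjustment; step 3 shows the fall.
- *That super-eLND means any resection beyond the template.* This is plausible, but the protocol does not say so. Section 5.2 also separates suspicious nodes that will be targeted from those outside the template, which are left to discretion.

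**Conclusion.** The point holds. As written, the comparison has no defined exposure and contradicts the one-group design. Given how section 5.2 makes dissections wider, it is confounded by disease extent, and baseline balance tests do not correct that. The direction of this conclusion follows from the text. Its size does not: the 20% and 42% false-rejection figures depend on assumed nodal proportions and effects.

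The three-level chi-square is clearly weaker than a baseline-adjusted score (about 44–66% v 76–91% at 90 v 30; 57–80% v 88–96% at 60 v 60), under an assumed 0.5 SD difference, a ±0.5 SD band and r of 0.5 to 0.7. Part of that gap comes from baseline adjustment. The mismatch of instrument and 2-month time point is a plain contradiction that needs no assumption. This is a secondary analysis that should be rewritten; it does not threaten the primary result.

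**What to change.** Rewrite the quality-of-life paragraph of section 7 b).

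1. Reconcile it with section 3.2. Either define extent of dissection for analysis from the operative packet record, before outcomes are examined, or drop the two-group comparison.
2. Align the instrument and time points with the EPIC schedule.
3. Analyse the continuous score adjusted for its baseline, by ANCOVA at a named visit or a mixed model over visits. Keep worsened/stable/improved as a descriptive table, with its limits stated.
4. Adjust the extent contrast, for both quality of life and complications, for pre-surgical PSA, clinical stage, grade and imaging status. Label it observational and exploratory.

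PSA, stage and grade are collected at referral (section 5.4), imaging precedes surgery, and packets are labelled and graded complete or incomplete (section 5.2). No new data are needed. The cost is revised wording, somewhat more modelling, and a categorical result that becomes descriptive. There is also a real statistical cost to state openly: if imaging-negative men never have wider dissection, the imaging-adjusted contrast rests on imaging-positive men alone. Overlap may be thin and power only about 33–74% under the assumptions above. If the overlap proves too small, description is the better choice.

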5.4. RECRUITMENT AND SCREENING

Participants have been referred to an urologist for a radical prostatectomy and lymph node dissection following a diagnosis of prostate cancer. The participant will be intermediate and high-risk cancer patients with a $\geq 10\%$ probability on LN where LND would currently be performed as part of the treatment protocol (guided by the updated Briganti nomogram) [34].

The participant will provide the following information as part of the referral and for assessment to participate:

- 99mTc bone scan and MRI scan of abdomen and pelvis
- Documentation of demographic variables
- Pre-prostatectomy PSA, clinical stage, grade
- Use of hormones or other therapies prior to prostatectomy

The urologist will then assess the participant for enrolment into the trial based on the inclusion and exclusion criteria. Should the participant meets the inclusion criteria and none of the exclusion criteria, the participant will be referred to the St Vincent's Nuclear Medicine Department for recruitment into the trial.

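### The added quality-of-life comparison of standard eLND with super-eLND is an unadjusted test on three change categories between non-randomised groups: it loses power and cannot separate surgery from disease extent

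*Protocol*

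**What the plan says.** Protocol section 7(b) names quality of life and complications as the secondary outcome. It gives three steps for quality of life, the last two of which set standard eLND against super-eLND.

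- First, "quality of life (as measured using EORTC-QLQ-C30) will be evaluated using one-way ANOVA". No baseline term or covariate is named.
- Second, "baseline characteristics will be compared between groups to assess whether the groups are balanced using Chi-square tests and Fisher's exact tests". Nothing is said about what follows if they are not balanced.
- Third, and described as additional, the plan is "comparing the change in quality of life scores (worsened, stable or improved quality of life) from baseline to 2 and 6 months". The same chi-square and Fisher's exact tests apply, and no covariate is named. Complications are to be handled in a similar way.

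The synopsis calls the study non-randomised, and section 3.2 describes a single study group. The term super-eLND occurs only in section 7(b). Section 5.2, item 3, is the one place that shows how a wider dissection could arise. Nodes suspicious on either scan are targeted in addition to the template, and, at the surgeons' discretion, "suspicious nodes outside this template may also be resected if doing so does not place the patient at significant additional risk". Section 5.4 lists "Pre-prostatectomy PSA, clinical stage, grade" among the items collected at referral.

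**The concern.** The text fixes a test for a group comparison without dealing with how the groups come about. If men receive the wider dissection because imaging suggests more nodal disease, and because the surgeon judges the added risk acceptable, the groups are likely to differ in prognosis, later treatment and starting quality of life. An unadjusted comparison then mixes those differences with the effect of the operation. Testing baseline balance does not help, because no action depends on the result.

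Separately, reducing a continuous score to three categories throws away information, and the test does not use the baseline score as a covariate. A secondary finding on the quality-of-life cost of wider dissection bears on the study's hypothesis that imaging should direct nodal treatment. Under the written analysis, a real effect is easier to miss and an apparent one is hard to interpret.

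**Working it through.** **Inputs.** From the protocol: 120 men (section 3.3). Two-sided alpha of 0.05 is stated only for the McNemar test in section 7(a) and is carried over here. The protocol gives no effect size, SD, group split, cut points or power for quality of life, so there is no planned figure to reproduce. Assumed: 30% super-eLND (84 v 36), a 0.5 SD effect, cut points at ±0.5 SD, and baseline-to-follow-up correlation r of 0.4 to 0.7.

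**Power of the continuous analyses (normal approximation).** With SD 1, the standard error of a difference in follow-up means is √(1/84 + 1/36) = 0.199, and 0.5/0.199 = 2.51.

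- One-way ANOVA on the follow-up score: Φ(2.51 − 1.96) = 71%, whatever r is.
- t-test on continuous change, SD √(2 − 2r): at r = 0.4, 0.6, 0.7 the ratio is 2.51/1.095, 2.51/0.894, 2.51/0.775 = 2.29, 2.81, 3.24, so power is 63%, 80%, 90%.
- Linear model with baseline score (ANCOVA), SD √(1 − r²): 2.51/0.917, 2.51/0.800, 2.51/0.714 = 2.74, 3.14, 3.51, so power is 78%, 88%, 94%.

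**Power of the three-category chi-square.** At r = 0.6 change has SD 0.894. The shares worsened/stable/improved are 29%/42%/29% in the standard group and 50%/37%/13% in the group shifted by −0.5. With 84 and 36 men the noncentrality on 2 df is 5.96, so power is 58%. Simulation agrees:

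| r | Chi-square (simulated) | t-test on change | ANOVA on follow-up | ANCOVA (simulated) |
|---|---|---|---|---|
| 0.4 | 42% | 63% | 71% | 77% |
| 0.6 | 60% | 80% | 71% | 88% |
| 0.7 | 72% | 90% | 71% | 94% |

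The gap between chi-square and the t-test on the same change score, 18 to 21 points, is the cost of categorising. The remaining 4 to 14 points up to ANCOVA come from using the baseline score better.

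**Dependence on the split.** With splits from 60:60 to 96:24 and r from 0.3 to 0.7, chi-square power ranges from 26% to 80%. It is below ANCOVA in every setting, by about 16 to 39 points.

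**Confounding by disease extent.** Split 80:40, r = 0.5, no surgical effect, and disease extent lowering follow-up quality of life in the wider-surgery group:

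| Disease-related deficit | Chi-square rejects | ANOVA on follow-up rejects | ANCOVA on baseline score only rejects |
|---|---|---|---|
| 0 | 5% | 5% | 5% |
| 0.2 SD | 11% | 18% | 23% |
| 0.3 SD | 21% | 33% | 43% |
| 0.5 SD | 52% | 73% | 83% |

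All three analyses attribute the deficit to surgery, and the more powerful ones do so more often. Adjusting for the baseline score alone therefore buys precision, not protection.

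**Groups that already differ at baseline.** Split 84:36, r = 0.6, no surgical effect, baseline gap of 0.3/0.5/0.8 SD:

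- If the gap shrinks towards the common mean by follow-up, chi-square on change rejects 8%/12%/26% and ANCOVA 5% throughout.
- If the gap simply persists, chi-square on change stays near 5% and ANCOVA rejects 12%/23%/47%.

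Which model applies cannot be told from the protocol.

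**The case against.** The strongest reply has four parts.

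- **The categorical test is not the only analysis.** The protocol calls it additional, and a score-level ANOVA precedes it. This stands. If the ANOVA is run on the follow-up score by group, it has about 70% power, and at r = 0.7 it does no better than the chi-square. So the 42% to 72% does not describe the whole plan. But the ANOVA names no covariate either, so it is equally open to confounding.
- **Group formation is inferred.** This also stands. A reader might conclude that the groups are defined by imaging. The protocol never defines super-eLND, and surgeon discretion and patient risk also enter. That adds a source of selection.
- **ANCOVA is not a cure.** A reader might infer that change from baseline is biased here while ANCOVA keeps false positives at 5%. That is true only if the baseline gap shrinks towards a common mean; if it persists, the ranking reverses. Nor do PSA, stage and grade necessarily capture nodal disease seen on imaging. If imaging nearly determines the operation, there may be too little overlap to adjust at all.
- **Detail may sit in an analysis plan, and the outcome is secondary.** Covariates are often left to such a plan, and three categories are easy to read. But the protocol itself fixes the unadjusted categorical test, so an adjusted analysis would depart from it. The primary accuracy analysis is unaffected.

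**Conclusion.** The point holds for what section 7(b) fixes: an unadjusted categorical comparison between undefined, non-randomised surgical groups, with a balance check that leads nowhere. Under the assumed inputs its power is 22 to 35 points below that of a baseline-adjusted linear model. The direction held in every setting tried; the size depends on the split, correlation, effect and cut points, none of which the protocol gives. Confounding by disease extent is a plausible consequence of section 5.2, not a demonstrated bias, and its size cannot be derived from the document.

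Two stronger conclusions are not supported: that ANCOVA would hold the false-positive rate at 5%, and that adjustment would remove confounding by disease extent. The point deserves correction because the fix is cheap, but it concerns a secondary outcome only.

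**What to change.** Rewrite the paragraph in section 7(b):

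1. Define standard eLND and super-eLND for the analysis, and reconcile the two groups with the single study group in section 3.2.
2. Make the group comparison a linear model on the continuous score at each follow-up time, with group, baseline score, PSA, clinical stage, grade and pre-operative imaging nodal extent. Examine overlap first, and include imaging extent only where both groups are represented. Report the adjusted difference with its 95% CI.
3. Give the unadjusted difference in continuous change as a sensitivity analysis, because neither approach is generally unbiased when non-randomised groups differ at baseline.
4. Replace the baseline significance tests with a descriptive table.
5. Keep worsened, stable and improved as description only, with stated cut points.
6. Label the result as an association, not an effect of surgery.

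The cost is a paragraph of wording, slightly more analysis and a more cautious conclusion. PSA, stage, grade and the scans are already collected. The baseline score is available if EPIC is analysed, since section 5.2 schedules it at baseline and 6 months. That section schedules neither the QLQ-C30 named in section 7(b) nor a 2-month survey, so instrument and time points must be reconciled before the model is fixed.

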After dissection, the specimens will be sent to pathology for histopathological examination. The lymph nodes will be reviewed at 2mm dissections. The result of histological examination of the lymph nodes (gold standard) will be compared with the result of 68Ga-PSMA PET scan and Nano MRL. Sensitivity, specificity, positive predictive value (PPV), and negative predictive value (NPV) for Nano MRL and Ga68-PSMA PET scan in pelvic lymph nodes with corresponding CT size measurement in comparison with histopathology will be assessed for detection of lymph node metastases.

Analysis will include assessing sensitivity, specificity, diagnostic accuracy, positive and negative predictive values for different levels of Nano MRL and PSMA PET avidity in pelvic lymph nodes with corresponding CT size measurement in comparison with histopathology.

5. *Re-imaging*

In participants where the 68Ga-PSMA PET and/or Nano MRL detected metastases in the lymph nodes but these were not seen in the histopathology (i.e., a false positive result), the participant will undergo a repeat PSA test, a 68Ga PSMA PET scan and a Nano MRL 6 weeks after the radical prostatectomy to confirm the accuracy of the original results and to ensure that no other sites of metastases missed. As noted in section 5.3, correspondence from [name] (Appendix D) and from clinical evidence to date, there have been no safety issues as a consequence of having a repeat 68Ga PSMA PET scan and/or a Nano MRL. All precautionary safety measures will be performed.

6. Follow up visits

As part of the participant's clinical care, follow up consultations with the treating urologist are planned for 6 weeks, 2 months, 6 months, 12 months and 24 months post surgery.

7. Quality of Life (QOL) survey

To determine the outcome of treatment, the participant will be asked to complete the self-reporting Expanded Prostate Cancer Index Composite (EPIC) survey. The EPIC survey has been extensively used to report on the physical, emotional and psychological outcomes of the prostate cancer patients. The participant will ask to complete the survey at baseline (prior to surgery), at 6 weeks, 3 months, 6 months, 1 year and then yearly for a minimum of 5 years.

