6. SAFETY

6.1. ADVERSE EVENT REPORTING

An adverse event to either 68Ga-PSMA PET Scan and/or Nano MRL will be considered as any unfavourable and unintended sign, symptom, or disease temporally associated with their use, whether or not they are directly related to the 68Ga-PSMA PET Scan and/or Nano MRL. Should an adverse event occur, it will be reported to the trial investigators, as well as documented in the participant's medical records.

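### Complications are a secondary outcome compared between two groups, but the protocol defines neither the score nor the groups, schedules no collection, and does not clearly cover surgical events in its adverse event definition

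*Protocol*

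**What the plan says.** Protocol section 7(b) states: "Secondary outcome of interest is quality of life and the complications". It sets out a comparison of quality-of-life scores "between the two groups (standard eLND versus super-eLND"), using Chi-square and Fisher's exact tests, and closes the paragraph with "Similar method will be used evaluating the differences in the complication score".

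Section 3.2 describes the design differently: "There will only be one study group".

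The surgery is partly directed by the trial's own imaging. Section 5.2, step 3, says: "Suspicious lymph nodes detected on nano-MRL or PSMA will be additionally targeted for resection during lymph node dissection, particularly presacral and mesorectal nodes". It adds: "Specifically identified nodes in the mesorectal plane may be localised with percutaneous hookwire prior to dissection". It also lets the surgeons remove suspicious nodes outside the template at their discretion.

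After surgery, section 5.2, step 6, says that "follow up consultations with the treating urologist are planned for 6 weeks, 2 months, 6 months, 12 months and 24 months post surgery". It does not say what is to be recorded at them.

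Section 6.1 treats as an adverse event to the PET scan or the Nano MRL "any unfavourable and unintended sign, symptom, or disease temporally associated with their use", with no causal link required. Section 6.2 defines serious adverse events by the usual seriousness criteria.

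**The concern.** A secondary outcome needs a variable, a time at which it is collected and, if it is to be compared, groups. Section 7(b) names a test for complications, but the protocol supplies none of these three. A later analysis plan could define a score, but it could not supply observations that were never made.

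The gap matters because some of the surgical risk comes from the trial. A suspicious node on either scan can lead to extra resection in the presacral or mesorectal region, sometimes after hookwire placement, and a false-positive image can do so with no disease present. The background section itself links extended lymphadenectomy with longer operations and a risk of complications. If non-serious complications are recorded unevenly, or only in hospital notes, the trial cannot describe reliably what this extra surgery cost the men who had it.

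**Working it through.** No arithmetic is involved: the protocol gives no complication rate, effect size or group size for this outcome. The check is whether each element that the analysis needs can be found in the text.

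1. **The variable.** The complication score is mentioned once, in section 7(b). No instrument, grading scale, assessor or time window is given there or elsewhere. Complications do not appear in the objectives (sections 2.1 and 2.2) or in the synopsis list of endpoints.

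2. **Collection.** Section 5.2 has seven steps: screening, imaging, surgery, histopathology, re-imaging, follow-up visits and the quality-of-life survey. None records a surgical complication. The surgical step requires each packet to be labelled and classed as complete or incomplete, which serves the concordance analysis. The five consultations list no assessment. The one patient-reported instrument scheduled is EPIC, a self-completed survey of physical, emotional and psychological outcomes; it may reflect functional effects but does not grade complications.

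3. **The groups.** Section 7(b) needs standard eLND and super-eLND. Super-eLND is not defined anywhere, no step assigns or classifies men to it, and section 3.2 provides for one group. Image-prompted resection in section 5.2 might be what is meant, but the protocol does not say so. It also does not ask for a record of which regions were dissected because of the images.

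4. **The safety section as a substitute.** Section 6.1 names two procedures, the PET scan and the Nano MRL, and does not name the prostatectomy, the node dissection or the hookwire. Section 5.3 covers only the two imaging agents. Surgery follows the Nano MRL by 7 to 10 days. Section 6.1 sets no time window, so whether a post-operative event counts as temporally associated with a scan is left to the reader. Events that do count go to the investigators and the medical record, without grading.

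5. **Serious events.** Section 6.2 is introduced as applying to medicines, but its text reaches any untoward occurrence that meets a criterion such as prolonged hospitalisation. The reporting form in Appendix B asks about relationship to an intervention or procedure as well as to a drug. A serious surgical complication can therefore be reported by this route.

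Taken together, serious surgical events have a plausible route, non-serious ones have no clear one, and nothing scheduled yields a graded score or a group label for the test in section 7(b).

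**The case against.** A reader might infer that harms of the dissection will go unmeasured, or that everything below the serious level is lost. The documents do not support that. Section 6.2 can capture serious surgical events, and several of the complications that matter most could meet its criteria. Section 6.1 has no window and asks for no causal link, so early post-operative events are not plainly excluded. Five consultations are planned, clinical follow-up at 24 months is a listed endpoint, and medical records will hold some information. The flow chart in section 5.1 is not readable in the text used here, and the initial assessment form (Form A) is not appended, so study forms may exist that cannot be seen. This limits the point to what the protocol specifies. It does not show that graded complication data will exist at both hospitals.

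A second tempting reading is that the score is to be analysed as change from baseline, which would be meaningless for a surgical complication. The wording about change describes quality of life. The complication sentence refers only to a similar method, which may mean just the between-group tests. The comparison still fails, because the variable and the groups are missing on either reading.

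A third is that the protocol's case for lower morbidity rests on these data. Section 1.2 ties lower morbidity to sparing men an unnecessary dissection. All men in this trial are planned for dissection, so complication counts here could not test that claim.

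It can also be said that the grading scale and the form of the estimates belong in an analysis plan or case report form, and that complications are absent from the objectives and endpoint list. Both are fair, and they keep the point to a secondary outcome. They do not excuse naming an outcome without scheduling its collection, or comparing two groups in a one-group design.

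**Conclusion.** The point holds in this form: the complication comparison in section 7(b) cannot be run from the data the protocol schedules, because the score is undefined, its collection is not scheduled, super-eLND is undefined and the design has one group. Non-serious complications of the dissection, including those of image-prompted resection and hookwire localisation, are not clearly or systematically recorded or graded. Capture of serious ones is plausible but depends on how sections 6.1 and 6.2 are read.

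The extent is one stated secondary outcome, in all 120 planned participants and at all five post-operative consultations. The comparison of imaging with histology is unaffected. This should be corrected, but it does not threaten the trial's main result.

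The conclusion assumes that no unseen flow chart entry or case report form already collects graded surgical complications. If one does, what remains is to cite it in the protocol, define the score and resolve the conflict over groups.

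**What to change.** - **Sections 6.1 and 5.2, step 6:** name the prostatectomy, the node dissection and hookwire localisation in event recording, with a stated time window. Record intra-operative and post-operative complications on a standard surgical grading scale at the existing early visits, for instance 6 weeks and 2 months.
- **Case report form:** record which regions were dissected because of imaging, and whether a hookwire was used.
- **Section 7(b):** replace the two-group test of a complication score with the proportion of men with any complication and the proportion with a higher-grade complication, each with a 95% confidence interval. Give these overall and by whether image-prompted regions were dissected. State that the second contrast is not randomised and is confounded by suspected nodal burden, so it is descriptive only.
- **Sections 3.2 and 7(b):** reconcile the two-group wording with the single-group design, by defining the groups or removing them.

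The overall estimate would be usable. With 120 men, the 95% half-width by the normal approximation is at most 1.96 × √(0.25/120) = 0.089, or about 9 percentage points. Estimates by image-prompted dissection will be wider, by an amount that cannot be given because the protocol does not say how many men are expected to have it.

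The cost is a page of data entry at visits already planned, plus the wording changes. No visit or procedure is added and no treatment is altered.
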